14.2.1. LABORATORY REFERENCE RANGES

Quantitative laboratory measurements will be compared with the relevant laboratory reference ranges and categorized as:

- Low: Below the lower limit of the laboratory reference range.
- Normal: Within the lower and upper limits of the laboratory reference range.
- High: Above the upper limit of the laboratory reference range.

Document:	K:\AAA\Ga-PSMA-R2\VYA27826\ Biostatistics\Documentation\SAP\v2.0\Ga-PSMA-R2-SAP_v2.0		
Author:	[Redacted]	Version Number:	2.0
Template No.:	CS_TP_BS016 Revision 5	Version Date:	29JUN2020
Effective Date:	01Apr2018	Reference:	CS_WI_BS005

14.2.2. SEVERITY GRADING FOR LABORATORY DATA

Laboratory results will be classified according to

- *The Toxicity Grading Scale for Healthy Adult and Adolescent Volunteers Enrolled in Preventive Vaccine Clinical Study.*
- *The Common Terminology Criteria for Adverse Events (CTCAE) Version 4.03*
- *The University of Delaware Criteria*

The "Grade 0" will be introduced to indicate that a certain laboratory value can be seen as "normal" and does not fulfill the criteria of severity grading either within the reference range or elevated in the other direction than defined in the APPENDIX 3.

Parameters flagged as "Medical Advisor Input Needed" in APPENDIX 3, will be graded as per medical advisor identification based on listings provided .

14.3. ECG EVALUATIONS

Results from the ECG (Electrocardiogram) will be included in the reporting of this study.

The following ECG parameters will be reported for this study:

- RR Interval (msec)
- PR Interval (msec)
- QRS Interval (msec)
- QT Interval (msec)
- QTcF Interval (msec)
- QTcB Interval (msec)
- Overall interpretations of ECG (Investigator's judgment):
 - Normal
 - Abnormal, Not Clinically Significant
 - Abnormal, Clinically Significant

The following summaries will be provided for ECG data:

- Actual and change from baseline by visit (for quantitative measurements)
- Incidence of markedly abnormal post-baseline values at any time post-baseline.
- Shift from baseline according to worst overall interpretation
- Box plots of absolute values over time and changes from baseline over time
- Listing of patients meeting markedly abnormal criteria

The handling of retests, unscheduled and end of study measurements is described in Section 6.4.

14.3.1. ECG MARKEDLY ABNORMAL CRITERIA

Markedly abnormal quantitative ECG measurements will be identified in accordance with the following

Document:	K:\AAA\Ga-PSMA-R2\VYA27826\ Biostatistics\Documentation\SAP\v2.0\Ga-PSMA-R2-SAP_v2.0
Author:	 Version Number: 2.0

Version Date: 29JUN2020

Template No.: CS_TP_BS016 Revision 5
 Effective Date: 01Apr2018

Reference: CS_WI_BS005

predefined markedly abnormal criteria:

- Absolute values for QT interval, QTcB interval and QTcF will be classified as:
 - > 450 msec
 - > 480 msec
 - > 500 msec
- Change from Baseline for QT interval, QTcB interval and QTcF will be classified as:
 - >30 msec increase from baseline
 - >60 msec increase from baseline

14.4. VITAL SIGNS

The following Vital Signs measurements will be reported for this study:

- Weight (kg)
- Systolic Blood Pressure (mmHg)
- Diastolic Blood Pressure (mmHg)
- Temperature (°C), considering that $^{\circ}\text{C} = (^{\circ}\text{F} - 32) / 1.8$
- Heart Rate (bpm)
- Respiratory Rate (resp/min)

The following summaries will be provided for vital signs data:

- Actual and change from baseline by visit
- Incidence of markedly abnormal values at any time post-baseline
- Shift from baseline according to markedly abnormal criteria by visit
- Box plots of absolute values over time and changes from baseline over time
- Listing of patients meeting markedly abnormal criteria

The handling of retests, unscheduled and end of study measurements is described in Section 6.4.

A list of Vital Signs measurements to be included in the outputs, and a severity grading system is included in APPENDIX 4.

14.5. ECOG

ECOG performance status at baseline and post-baseline visits will be listed on the FAS.

15. BIODISTRIBUTION, DOSIMETRY AND IMAGING OF ⁶⁸GA-PSMA-R2

Biodistribution is defined as the activity in various organs over time quantified by imaging. Dosimetry is the assessment of radiation dose per unit administered activity.

Document: K:\AAA\Ga-PSMA-R2\VYA27826\ Biostatistics\Documentation\SAP\v2.0\Ga-PSMA-R2-SAP_v2.0
 Author:  Version Number: 2.0

Version Date: 29JUN2020

Template No.: CS_TP_BS016 Revision 5
 Effective Date: 01Apr2018

Reference: CS_WI_BS005

Biodistribution, dosimetry and imaging data are not collected in the CRF. Biodistribution and dosimetry data will be received from the principal scientist of a third-party radiation dosimetry vendor while imaging data will directly be sent from a third-party medical imaging vendor. Results from the radiation dosimetry vendor will be included in the reporting of Phase I of this study. Results from the medical imaging vendor will be included in the reporting of Phase I and II of this study. The analysis of imaging data will also be performed on patients from Phase I.

The terminology, conventional scans and standard imaging, both relate to CT, MRI and/or bone scans.

A list of tests and organs to be included in the outputs is included in APPENDIX 5.

15.1. ANALYSES OF BIODISTRIBUTION AND DOSIMETRY

For phase I, PET and conventional scans will be performed on Day 1 at 20-30 minutes, and 1, 2, and 3 – 4 hours post-injection. For Phase II, all patients will undergo whole body PET and conventional scans optimized for time (up to 2 time points) according to the data analysis from the Phase I component of the study. Further details about imaging assessments can be found in the section 6.5.4 of the protocol.

Data from the radiation dosimetry vendor will be presented using SI Units and the following statistical summaries will be provided:

- Decay corrected tissue activity in normal organs by timepoint
- Non-decay corrected tissue activity in normal organs by timepoint
- Residence times in normal organs
- Absorbed doses, whole body dose and effective dose of 68Ga-PSMA-R2 in normal organs

Time Activity Curve (TAC) will be produced as graphical representation of Decay corrected tissue activity and Non-decay corrected tissue activity.

15.2. ANALYSES OF IMAGING

15.2.1. LABORATORY OPTIMAL THRESHOLD

Standard uptake value (SUV) will only be available in PET scans.

Descriptive analysis will be performed on SUV and the following summaries will be produced:

- SUV_{max}, SUV_{mean} and TBR with positive lesion status in PET scan
- SUV_{max}, SUV_{mean} and TBR with positive lesion status in PET scan and correlated with conventional scan
- SUV_{max}, SUV_{mean} and TBR with positive lesion status in PET scan and not correlated with conventional scan

Lesion Tumor to Background Ratio (TBR) is defined as $SUV_{max(lesion)} / SUV_{mean(pluteal\ or\ thigh)}$ and will be summarized in the same way as SUV_{max} and SUV_{mean}.

Document: K:\AAA\Ga-PSMA-R2\VYA27826\ Biostatistics\Documentation\SAP\v2.0\Ga-PSMA-R2-SAP_v2.0
 Author: [Redacted] Version Number: 2.0

Version Date: 29JUN2020

Template No.: CS_TP_BS016 Revision 5
Effective Date: 01Apr2018

Reference: CS_WI_BS005

15.2.2. LESIONS DETECTED BY PET SCAN AND/OR CONVENTIONAL SCAN, BY TBR

The number of positive lesions detected by PET scan, correlated or not with conventional scan, will be presented by TBR category.

15.2.3. BURDEN AND LOCATION OF TUMOR LESIONS DETECTED BY ⁶⁸Ga-PSMA-R2 IN COMPARISON WITH CONVENTIONAL IMAGING MODALITIES SUCH AS CT/MRI AND/OR BONE SCAN.

- The difference of number of lesions detected by ⁶⁸Ga-PSMA-R2 PET scan and by conventional scan modalities such as CT/MRI and/or bone scan, will be displayed by location. The number of lesions detected on the PET scan, correlated and not correlated with conventional scan lesions, will be presented. The number of lesions detected on the conventional scan, not correlated with lesions detected on the PET scan, will be presented.
- The difference in the number of positive patients detected by ⁶⁸Ga-PSMA-R2 PET and by conventional scan modalities such as CT/MRI and/or bone scan, will be displayed by location. The number of positive patients detected on the PET scan, with at least 1 lesion correlated, and at least 1 lesion not correlated with a lesion detected on the conventional scan, will be presented. The number of positive patients detected on the conventional scan, with no lesions correlated with any lesion detected on the PET scan, will be presented. Note: A positive patient has at least 1 lesion detected.

15.2.4. CALCULATION OF PATIENT LEVEL AGREEMENT OF ⁶⁸Ga-PSMA-R2 PET IMAGING WITH CONVENTIONAL IMAGING IN PROSTATE CANCER PATIENTS

The patient level agreement is commonly used to characterize the agreement of a new test with the non-reference standard. Here ⁶⁸Ga-PSMA-R2 PET scan is the new test and conventional scan is the non-reference Standard.

		Conventional Scan	
		+	-
⁶⁸ Ga-PSMA-R2 PET Scan	+	a	b
	-	c	d
Total		a+c	b+d

The patient-level positive percent agreement, negative percent agreement and overall percent agreement will be calculated based on the number of patients with at least one positive lesion detected by conventional scan and/or at least one positive lesion detected by PET scan.

Document: K:\AAA\Ga-PSMA-R2\VYA27826\ Biostatistics\Documentation\SAP\v2.0\Ga-PSMA-R2-SAP_v2.0
 Author:  Version Number: 2.0

Version Date: 29JUN2020

Template No.: CS_TP_BS016 Revision 5
 Effective Date: 01Apr2018

Reference: CS_WI_BS005

These percent agreements will be calculated as follows with their two-sided 95% score confidence intervals:

- Positive percent agreement: $a/(a+c) * 100$
- Negative percent agreement: $d/(b+d) * 100$
- Overall percent agreement: $(a+d)/(a+b+c+d) * 100$

Where

- a is the number of patients with at least one positive lesion detected by conventional scan and at least one positive lesion detected by PET scan
- b is the number of patients with at least one positive lesion detected by PET scan that is not correlated with conventional scan
- c is the number of patients with at least one positive lesion detected by conventional scan that is not correlated with PET scan
- d is the number of patients with no lesions detected by conventional scan or PET scan

These 3 coefficients and their 95% Clopper Pearson Exact confidence intervals will be calculated using SAS PROC FREQ as follow:

```
PROC FREQ data=temp;
  tables resp/binomial (exact level='1');
RUN;
```

The lesion-level positive percent agreement and overall percent agreement will be calculated based on the number of lesions detected as positive by conventional scan and/or by PET scan.

These percent agreements will be calculated as follows with their two-sided 95% score confidence intervals:

- Positive percent agreement: $a/(a+c) * 100$
- Overall percent agreement: $(a)/(a+b+c) * 100$

Where

- a is the number of lesions detected as positive in both PET and conventional scan
- b is the number of lesions detected as positive in PET scan but not correlated with conventional scan
- c is the number of lesions detected as positive in conventional scan but not correlated with PET scan

These 2 coefficients and their 95% Clopper Pearson Exact confidence intervals will be calculated using SAS PROC FREQ as above.

Document: K:\AAA\Ga-PSMA-R2\VYA27826\Biostatistics\Documentation\SAP\v2.0\Ga-PSMA-R2-SAP_v2.0
 Author:  Version Number: 2.0

Version Date: 29JUN2020

Template No.: CS_TP_BS016 Revision 5
 Effective Date: 01Apr2018

Reference: CS_WI_BS005

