8.2.3. Preliminary Targeting Properties of ⁶⁸Ga-PSMA-R2 PET Imaging

The number and location of lesions identified by ⁶⁸Ga-PSMA-R2 PET imaging will be summarized and compared with those identified with conventional imaging techniques. Tumor uptake will be evaluated by SUV. SUV_{mean} and SUV_{max} will be determined along with tumor to background ratio and these will be summarized descriptively. Positive and negative lesions by the two imaging techniques will be cross tabulated overall and by localization area on a lesion level and a patient level. Agreement calculations for ⁶⁸Ga-PSMA-R2 imaging relative to conventional techniques will be performed on a patient level and summarized descriptively. Tests of association may be performed where appropriate.

Preliminary explorations of ⁶⁸Ga-PSMA-R2 imaging results relative to cytology and/or histopathology findings from archival and/or recent biopsy specimens will be performed for patients with biopsy data available.

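### SAP 15.2.3: the patient-level breakdown counts any unmatched PET lesion, but a conventional-scan patient only when nothing is matched, so partial PET misses are left out of it

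*SAP*

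**What the plan says.** SAP 15.2.3 has two bullets. The first works at lesion level and reports unmatched lesions for both methods. For conventional imaging it says: "The number of lesions detected on the conventional scan, not correlated with lesions detected on the PET scan, will be presented".

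The second works at patient level, by location. It opens with a comparison, "The difference in the number of positive patients detected by" PET and by conventional imaging, and closes with a definition that serves both methods: "Note: A positive patient has at least 1 lesion detected". Between these stand two sentences that break the positive patients down:

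- PET side: positive patients "with at least 1 lesion correlated, and at least 1 lesion not correlated with a lesion detected on the conventional scan".
- Conventional side: "positive patients detected on the conventional scan, with no lesions correlated with any lesion detected on the PET scan".

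SAP 15.2.4 then defines an overall patient-level table, not split by location. There "c is the number of patients with at least one positive lesion detected by conventional scan that is not correlated with PET scan", and cell b is its mirror image for PET.

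Protocol 8.2.3 asks for positive and negative lesions by the two techniques to be "cross tabulated overall and by localization area on a lesion level and a patient level".

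**The concern.** The two breakdown sentences set different thresholds. A single unmatched lesion is enough on the PET side. On the conventional side every lesion must be unmatched. A patient with one matched lesion and five conventional lesions that PET missed is in no conventional row. A patient with one matched lesion and one extra PET lesion is in the PET row.

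The departure looks unintended, because the lesion-level bullet and cells b and c of 15.2.4 treat the two methods alike. It matters because burden and location of lesions against standard imaging is a named secondary endpoint (Protocol 2.2.2), and this bullet is the only SAP output that is both patient-level and by location. A reader who sets the two rows side by side would see PET adding disease in many patients and missing it in few, whatever the real balance.

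**Working it through.** SAP 15.2.3 states no figure to reproduce, so the check is of the counting rules.

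**Fixed example.** Take 12 patients, each with 3 matched lesions, 1 lesion seen only on PET and 1 seen only on conventional imaging. The methods are equally discordant.

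- PET row, at least 1 uncorrelated lesion: 12 patients.
- Conventional row, no correlated lesion: 0 patients.
- Conventional row under the PET rule: 12 patients.
- Difference in positive patients: 12 − 12 = 0.
- Lesion-level bullet: 12 × 4 = 48 lesions on each scan, 12 × 1 = 12 of them unmatched on each.
- Cell c of 15.2.4 as its text defines it: 12 patients.

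The distortion is confined to the patient-level breakdown.

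**Expected counts.** Inputs:

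- Number of patients: 12, the cap on the mPCa group (Protocol 3.1).
- k, lesions per patient on each scan: not given; assumed 1 to 5.
- p, probability that a lesion is matched: not given; assumed 0.5 to 0.9, equal for both methods and independent between lesions.

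Formulas:

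- Patients with at least 1 uncorrelated lesion: 12 × (1 − p^k).
- Patients with no correlated lesion: 12 × (1 − p)^k.

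For p = 0.7 and k = 3: 12 × (1 − 0.343) = 7.9 and 12 × 0.027 = 0.3.

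Each cell shows PET row / conventional row under the SAP wording, reading the PET sentence as separate counts:

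| k | p = 0.9 | p = 0.8 | p = 0.7 | p = 0.5 |
|---|---|---|---|---|
| 1 | 1.2 / 1.2 | 2.4 / 2.4 | 3.6 / 3.6 | 6.0 / 6.0 |
| 2 | 2.3 / 0.1 | 4.3 / 0.5 | 6.1 / 1.1 | 9.0 / 3.0 |
| 3 | 3.3 / 0.01 | 5.9 / 0.1 | 7.9 / 0.3 | 10.5 / 1.5 |
| 5 | 4.9 / <0.01 | 8.1 / <0.01 | 10.0 / 0.03 | 11.6 / 0.4 |

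Under one common rule the two numbers in every cell would be equal. At one lesion the two rules coincide; the gap appears from two lesions upward.

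**The other reading of the PET sentence.** It can also mean one joint category: at least 1 correlated and at least 1 uncorrelated lesion in the same patient. The expected PET count is then 12 × (1 − p^k − (1 − p)^k). At p = 0.7 this gives 0, 5.0 and 7.6 for k = 1, 2 and 3, against 3.6, 1.1 and 0.3 on the conventional side. The two sides still differ, but at one lesion the direction reverses, and a patient whose PET lesions are all unmatched is not counted on the PET side.

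**Who is affected.** PCa-BR patients, about 6 + 12 = 18 of 30, must have no lesion on CT/MRI or bone scan at entry (Protocol 4.1, criterion 3a). Unless a later read finds some, the conventional row concerns mainly the mPCa group.

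**The case against.** A reader might infer that PET misses vanish from the analysis, or that the planned comparison of the two methods is itself biased towards PET. The documents support neither. Every conventional lesion without a PET match is reported in the first bullet of 15.2.3. Cell c of 15.2.4 counts patients with at least one such lesion, and its lesion-level counterpart puts missed lesions into both agreement denominators. The comparison that the bullet names is the difference in positive patients, which applies one definition to both methods. The SAP never labels the two rows PET-only and conventional-only, nor does it say that they should be contrasted.

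There is also an innocent reason for the wording. If matching is mutual, patients with at least 1 correlated lesion plus conventional-positive patients with none make up all conventional-positive patients, so the conventional row may be there only to complete that total.

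Three limits on size also stand. If matching is judged within each location, k is lesions per location, which is smaller and may often be 1. The output is descriptive, since SAP 6.6 plans no formal testing. SAP 8 leaves table content to templates that are not in the documents, so the missing row could exist there.

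These points narrow the concern but do not remove it. Lesion totals cannot show how many patients had a missed lesion: 12 missed lesions may belong to 1 patient or to 12. Cell c is not by location. The difference in positive patients is 0 whenever every patient is positive on both scans, however much each scan misses. Completing the total still leaves no row for partial PET misses.

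**Conclusion.** The asymmetry is in the text. In patients with several lesions, the patient-level breakdown of 15.2.3 omits partial PET misses while counting the corresponding extra PET lesions. With the PET sentence read as separate counts and the methods performing equally, the gap among 12 patients at a match probability of 0.7 is nil at one lesion, about 5 patients at two (6.1 against 1.1) and 7.6 at three (7.9 against 0.3). These sizes rest on assumed lesion counts, assumed match rates and independence between lesions. The plan does allow for several lesions per patient (up to 10 for dosimetry in Protocol 6.5.4.2), but it gives no expected number.

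The point is limited to one descriptive breakdown of a secondary endpoint and mainly to the mPCa group. It does not touch the primary safety objective, the lesion-level counts, the overall cell c or the difference in positive patients. The wording should be changed, because as it stands the breakdown can mislead, and the PET sentence and the unit of matching are both open to more than one reading.

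**What to change.** In the second bullet of SAP 15.2.3, keep the opening comparison and the closing Note that defines a positive patient. Replace the two sentences before the Note with:

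> For each method, by location and overall, the number of positive patients with (i) at least 1 lesion correlated with the other method, (ii) at least 1 lesion not correlated, and (iii) no lesion correlated will be presented as separate counts; in the by-location rows, correlation is judged among the lesions in that location.

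This gives both methods the same rows, removes the joint-category reading and fixes the unit. Any table template should be brought into line. The correlation status of each lesion is already used throughout SAP 15.2, so no new data are needed. The cost is a few extra table rows and a result that may look less favourable to PET.

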4.1. Inclusion Criteria

- 1. Males, 18 years or older
- 2. Signed and dated written informed consent by the patient prior to any study-specific procedures.
- 3. Histologically confirmed adenocarcinoma of the prostate.
 - a. biochemical recurrence: defined as PSA is ≥ 0.2 ng/mL after radical prostatectomy or PSA nadir plus 2 ng/mL after radiation therapy with corresponding CT/MRI or bone scan revealing absence of local recurrence or metastatic lesions.

OR

- b. metastatic disease: defined as both, castration-sensitive or castration-resistant mPCa (presence of at least one metastatic lymph-node, visceral metastasis and/or bone metastasis).
- c. At least 2 weeks must have elapsed between last anti-cancer treatment administration and the administration of the imaging product, ⁶⁸Ga-PSMA-R2.
- 4. Prior major surgery must be at least 12 weeks prior to study entry.
- 5. Eastern Cooperative Oncology Group (ECOG) performance status 0-2, with a life expectancy ≥ 6 months.
- 6. Adequate bone marrow reserve and organ function as demonstrated by complete blood count, and biochemistry in blood and urine at Screening:
 - Hemoglobin (Hb): >8.0g/dL

- Platelet count of $> 50.000/\text{mm}^3$
- Serum creatinine < 1.5 ´ upper limit normal (ULN) or estimated glomerular filtration rate (eGFR) > 50 mL/min based upon The Chronic Kidney Disease Epidemiology Collaboration (CKD-EPI) equation.
- 8. For male patients with partners of childbearing potential, agreement to use barrier contraceptive method (condom) and to continue its use for 28 days after IP administration.

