6.5.2. CT/MRI/Bone Scan

All patients are required to undergo a CT/MRI within 2 months prior to enrollment. If a CT is performed, this should be a standard diagnostic thoracic and abdominopelvic CT scan, with a slice thickness of ≤ 5 mm; if MRI is performed, the injection of a contrast medium is recommended. Standard imaging modality for patients with PCa in biochemical relapse or with

metastatic disease, as applicable, will be performed as per routine institutional practice. Per RECIST v1.1 the imaging modality must be consistent throughout the study. Tumor assessment imaging procedures will be performed per local practice. CT scan is the preferred method and MRI will be done per local standard-of-care. Patients with either previous history of metastatic disease to the bone or any symptoms indicative of metastatic bone disease will require a bone scan.

All patients with metastatic prostate cancer enrolled in Phase 2 portion of the study will have their imaging procedures assessed locally for clinical management and centrally for comparison with ⁶⁸Ga-PSMA-R2 PET imaging.

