6. GENERAL CONSIDERATIONS

6.1. POPULATION SUMMARIZATION

In general, data will be presented by population.

- The following populations will be used in the analyses:

Document:	K:\AAA\Ga-PSMA-R2\VYA27826\ Biostatistics\Documentation\SAP\v2.0\Ga-PSMA-R2-SAP_v2.0
Author:	[Redacted] Version Number: 2.0
Template No.:	CS_TP_BS016 Revision 5
Effective Date:	01Apr2018
Version Date:	29JUN2020
Reference:	CS_WI_BS005

- PCa-BR
- mPCa
- The PCa-BR population group will also be presented separately for Phase I and Phase II patients.

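### On the entry read, positive agreement cannot be estimated in biochemical relapse, and overall agreement there is just the share of patients in whom PET finds nothing

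*SAP*

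**What the plan says.** Patient-level agreement of PET with conventional imaging is a secondary objective and endpoint (Protocol 2.1.2 and 2.2.2; SAP 2.2). SAP 15.2.4 lays out a 2×2 table of PET (rows) against conventional scan (columns) with cells a to d. From it the SAP derives positive agreement a/(a+c), negative agreement d/(b+d), and "Overall percent agreement: $(a+d)/(a+b+c+d) * 100".

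On presentation, SAP 6.1 states: "In general, data will be presented by population". Appendix 1 lists the columns as PCa-BR, mPCa and Overall.

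The entry criteria in Protocol 4.1 bear directly on the comparator:

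- Criterion 3a takes patients with PSA relapse "with corresponding CT/MRI or bone scan revealing absence of local recurrence or metastatic lesions".
- Criterion 3b defines metastatic disease by "presence of at least one metastatic lymph-node, visceral metastasis and/or bone metastasis". It does not name the scan that must show it.

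Protocol 6.5.2 adds: "All patients are required to undergo a CT/MRI within 2 months prior to enrollment". It also provides for a central assessment of imaging, for comparison with PET, in Phase 2 mPCa patients.

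Protocol 8.1 illustrates precision with 25 of 30 patients having PET-detected lesions. It calls this 83.3% patient-level agreement, with a 95% CI of 66.4% to 92.7%.

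Neither document says which coefficient can be estimated in which group, or what to report when a denominator is zero.

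**The concern.** Agreement with a comparator is informative only if the comparator can vary. In PCa-BR its value is a condition of entry.

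The direction of the measure also matters. Protocol sections 1 and 1.1 describe the limits of conventional imaging and the importance of localising disease at biochemical recurrence, and section 1.2 proposes the product for diagnosis in that setting. A PCa-BR patient in whom PET shows disease that CT or MRI did not show is the hoped-for result, yet the formula counts that patient as a disagreement.

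Run as written, the PCa-BR column would hold one empty coefficient and two that fall as PET detects more. The Overall column would give a percentage that a reader could take for imaging performance.

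**Working it through.** **1. The plan's own figure.** The Wilson score interval is (p + z²/2n ± z√(p(1−p)/n + z²/4n²)) / (1 + z²/n). With p = 25/30, n = 30 and z = 1.96 it gives 66.4% to 92.7%, which matches Protocol 8.1. Clopper-Pearson would give 65.3% to 94.4%. The interval is correct; the question is what 25/30 measures.

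**2. Inputs.** PCa-BR: 6 (Phase 1) + 12 (Phase 2) = 18. mPCa: 12. Total 30 (Protocol 3.1). Assume a proper 2×2 table in which all 18 PCa-BR patients are scan-negative (criterion 3a) and all 12 mPCa patients are scan-positive (expected from 3b). Let r be the number of PCa-BR patients and m the number of mPCa patients who are PET-positive.

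**3. Coefficients by group.**

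| | a | b | c | d | Positive | Negative | Overall |
|---|---|---|---|---|---|---|---|
| PCa-BR | 0 | r | 0 | 18−r | 0/0 | (18−r)/18 | (18−r)/18 |
| mPCa | m | 0 | 12−m | 0 | m/12 | 0/0 | m/12 |
| Pooled | m | r | 12−m | 18−r | m/12 | (18−r)/18 | (m+18−r)/30 |

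Pooled positive agreement is the mPCa PET-positive rate. Pooled negative agreement is the PCa-BR PET-negative rate. Pooled overall agreement is (12/30)(m/12) + (18/30)((18−r)/18), a 12:18 mix of the two.

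**4. Direction and size.** One more PET-positive PCa-BR patient changes overall agreement by −1/18 = −5.6 points in PCa-BR and −1/30 = −3.3 points pooled. One more PET-positive mPCa patient changes the pooled figure by +3.3 points.

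With m = 12:

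| r | PCa-BR overall | Pooled overall |
|---|---|---|
| 0 | 100.0% | 100.0% |
| 6 | 66.7% | 80.0% |
| 9 | 50.0% | 70.0% |
| 13 | 27.8% | 56.7% |
| 18 | 0.0% | 40.0% |

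With r = 9, the pooled figure rises from 56.7% (m = 8) to 63.3% (m = 10) and 70.0% (m = 12). At the extremes, PET positive in nobody gives (0+18−0)/30 = 60.0%, and PET positive in everybody gives (12+18−18)/30 = 40.0%.

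**5. The 8.1 example under the SAP formula.** If m + r = 25, then m lies between 7 and 12, and overall agreement is (m+18−(25−m))/30 = (2m−7)/30. This runs from 7/30 = 23.3% (m = 7, r = 18) to 17/30 = 56.7% (m = 12, r = 13). It cannot be 83.3%. Conversely, agreement of 25/30 requires m − r = 7, so at most 12 + 5 = 17 patients could be PET-positive.

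**6. Cells as worded.** SAP 15.2.4 puts a patient in b for any PET lesion without a match on the conventional scan, and in c for any conventional lesion without a match on PET. A patient in a can therefore also be in b or c. Suppose all 12 mPCa patients are in a and 6 of them have an extra PET-only lesion. The cells then total 18, overall agreement is 12/18 = 66.7%, and negative agreement is 0/6 = 0%. Separately, the sentence naming the patients on whom agreement is based covers only those positive on at least one modality. Read literally, it excludes d, and PCa-BR overall agreement is then 0/r = 0% for any r above zero.

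**The case against.** **The comparison read need not be the eligibility read.** Imaging data come from a third-party vendor (SAP 15), and Protocol 6.5.2 provides a central read for Phase 2 mPCa. Criterion 3a accepts CT/MRI or bone scan, while the SAP comparator is CT, MRI and/or bone scan. This stands: a+c = 0 in PCa-BR is fixed on the eligibility read and expected, but not guaranteed, on the vendor read. A few reversed reads would leave a denominator of only those few patients.

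**mPCa.** A reader might infer that negative agreement must be undefined there. The documents do not support that. Criterion 3b names no scan, a central read could be negative, and cell b as worded can be above zero, giving 0% rather than 0/0. Few or no scan-negative mPCa patients is the expected result, no more.

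**Direction.** A reader might also infer that overall agreement falls whenever PET finds more disease. On a proper 2×2 table this holds only in PCa-BR; in mPCa, more detection raises it. Nor would a tracer that finds nothing pass unnoticed, because positive agreement of 0% in mPCa would be printed alongside.

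**Other outputs.** SAP 15.2.3 already plans counts of PET-positive patients by location, and 15.2.4 plans lesion-level agreement. It would be too strong to say that the trial yields no evidence on imaging. What these outputs lack is a single patient-level PCa-BR detection rate with an interval.

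**Biopsy.** Protocol 8.2.3 foresees "Preliminary explorations of ⁶⁸Ga-PSMA-R2 imaging results relative to cytology and/or histopathology findings", and SAP 15.2 describes no such output. This is a separate, minor omission. No new biopsy is required, and the table templates are not in the documents.

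**Importance.** The analysis is descriptive and secondary, with no formal testing (SAP 6.6), and the SAP itself calls conventional imaging a non-reference standard. That limits the consequence but does not make the statistic interpretable.

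**Conclusion.** The point holds for PCa-BR and for pooled overall agreement. On the eligibility read, positive agreement in PCa-BR has no denominator. Negative and overall agreement there are both the PET-negative rate, so they move against detection in 18 of the 30 planned patients. Pooled overall agreement is a weighted mix of opposite-direction quantities and cannot be read as performance. The 8.1 precision example describes a different quantity from the one SAP 15.2.4 computes.

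Pooled negative agreement is a different case. It is essentially 1 minus the PCa-BR detection rate and is not a product of the group sizes.

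The figures assume full planned enrolment, conventional scans that match entry status in both groups, and mutually exclusive cells. Central reads that differ from entry would shift them by a few patients without restoring a useful denominator.

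**What to change.** Amend SAP 15.2.4 and its table shells:

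1. Report patient-level positive percent agreement in mPCa.
2. In PCa-BR, replace the agreement coefficients with the patient-level PET detection rate and its 95% CI. State that conventional imaging is negative by entry, and list any patient whose central read differs. Call it a detection rate, since PET findings are not verified by this comparison.
3. Drop pooled overall agreement, or footnote it as a mix of opposite-direction quantities weighted by group size. If pooled negative agreement is kept, label it as essentially 1 minus the PCa-BR detection rate.
4. Define a to d as mutually exclusive by each patient's PET status and conventional-scan status, and include d explicitly in the base.

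Two small items belong in the same edit. Note that the 25/30 example in Protocol 8.1 is a detection rate. Name one interval method, because 15.2.4 says both "These percent agreements will be calculated as follows with their two-sided 95% score confidence intervals" and "These 3 coefficients and their 95% Clopper Pearson Exact confidence intervals will be calculated using SAS PROC FREQ as follow". Precision will then rest on 12 or 18 patients rather than 30; for example, 12 of 12 in mPCa has a score interval of 75.8% to 100.0%.

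The cost is SAP text and table shells, with no new data. The downside is the loss of one headline overall agreement figure. The primary safety analysis does not change.
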